*Provide a statement that the trial will be conducted in compliance with the protocol, International Council on Harmonization Good Clinical Practice (ICH GCP) and applicable state, local and federal regulatory requirements. Each engaged institution must have a current Federal-Wide Assurance (FWA) issued by the Office for Human Research Protections (OHRP) and must provide this protocol and the associated informed consent documents and recruitment materials for review and approval by an appropriate Institutional Review Board (IRB) or Ethics Committee (EC) registered with OHRP. Any amendments to the protocol or consent materials must also be approved before implementation. Select one of the two statements below. If the study is an **intramural** NIH study, use the second statement below:*

The trial will be conducted in accordance with International Council on Harmonization Good Clinical Practice (ICH GCP), applicable United States (US) Code of Federal Regulations (CFR), and the [specify NIH Institute or Center (IC)] Terms and Conditions of Award. The Principal Investigator will assure that no deviation from, or changes to the protocol will take place without prior agreement from the funding agency and documented approval from the Institutional Review Board (IRB), and the Investigational New Drug (IND) or Investigational Device Exemption (IDE) sponsor, if applicable, except where necessary to eliminate an immediate hazard(s) to the trial participants. All personnel involved in the conduct of this study have completed Human Subjects Protection and ICH GCP Training.

The protocol, informed consent form(s), recruitment materials, and all participant materials will be submitted to the IRB for review and approval. Approval of both the protocol and the consent form(s) must be obtained before any participant is consented. Any amendment to the protocol will require review and approval by the IRB before the changes are implemented to the study. All changes to the consent form(s) will be IRB approved; a determination will be made regarding whether a new consent needs to be obtained from participants who provided consent, using a previously approved consent form.

1 PROTOCOL SUMMARY

1.1 SYNOPSIS

Title: Utilizing Advances in Digital Inhaler Technology to Understand Heterogeneous Treatment Responses to Biologics in Severe Asthma

Study Description: This real-world study aims to determine baseline inhalation parameters and patterns of use in patients receiving treatment with TEVA digital inhalers, and to develop predictive models for asthma exacerbations and response to biologics using data collected from these devices.

Objectives:

Primary Objective:
To determine the baseline inhalation parameters and patterns of use of both the maintenance (AirDuo®) Digihaler™ and rescue (ProAir®) Digihaler™ in patients with severe persistent asthma who are being treated with biologics.

Secondary Objectives:

1. To determine the predictive value of inhalation parameters, including peak inspiratory flow (PIF), inspiratory time and volume, and number of inhaled doses on asthma exacerbations in a population of severe asthma patients on biologics.
2. To determine whether inhalation measurements can serve as surrogates of standard expiratory flow measurements. Specifically, to determine the correlation between PIF with FEV1 and identify thresholds for changes in PIF that are associated with a clinically meaningful increases or decreases (10%) in lung function as measured by conventional spirometry (e.g., FEV1).
3. To determine the impact of variable degrees of adherence to maintenance therapy on outcomes to biologics. The Digihaler™ will allow us to collect accurate information on adherence that will be utilized to divide patients into groups and to assess asthma outcomes such as change in mean FEV1, exacerbations, oral steroid reduction, and asthma control (using the asthma control test scores over time) in patients receiving biologic therapies.
4. To determine the impact on inhalation parameters on categorical response to biologics. Response will be categorized as non-response, partial and complete response on the basis of six factors: a 50% reduction in exacerbations, any reduction in maintenance OCS dose, change of at least 10% in FEV1, improvement of 3 points in ACT score, and patient perception of global improvement in asthma.

Exploratory Objectives

5. To evaluate the asthma control and health care utilization of subjects as measured by the number of exacerbations (acute worsening of asthma requiring at least 3 days of corticosteroids or a doubling dose of maintenance steroids), Emergency and hospitalization encounters, and patient-reported perceptions of asthma control.
6. To employ machine learning techniques to a robust well characterized cohort with clinical, biological, and digital markers to develop a predictive algorithm aimed at identifying responders to biologics. In addition, we would aim to develop an algorithm that can detect early changes in measured parameters that can predict long-term improvements in asthma control and exacerbations when biologics are initiated. The latter objective will be achieved by focusing on the subgroup of patients initiating biologics for the first time or switching between biologics due to perceived inadequate response.

Endpoints:

Primary Endpoint:

Mean and median number of (daily) doses of ProAir® Digihaler™ and AirDuo® Digihaler™ utilized at baseline, temporal patterns in rescue and controller medication utilization, and within-patient parameter mean, median, and variance per-inhalation to establish baselines.

Secondary Endpoints:

1. Proportion of patients with different rates of adherence.
2. Proportion of Patients achieving non-response, partial-responses, and complete response to biologics.
3. Change in Main Peak Inspiratory volume from baseline up to one year.
4. Change in Mean Inspiratory Time from baseline up to one year.
5. Change in mean peak inspiratory flow (PIF) from baseline up to one year.
6. Change in mean forced expiratory volume in one second (FEV1) from baseline up to one year.

Exploratory Endpoints

7. Number of exacerbations from baseline up to one year.
8. Number of hospitalizations.

9. Number of emergency room visits.
10. Mean Asthma Control Test (ACT) scores.
11. Algorithm that produces a daily asthma exacerbation probability given a set of baseline and current inhalation parameters. A confusion matrix summarizing the algorithm's performance on training dataset and from which performance statistics (accuracy, sensitivity, specificity, etc.) can be computed.
12. Machine learning model developed for predicting responders to biologics (developed in collaboration with the University of Michigan Morphomic Analysis Group). Reporting key factors in the model that are associated with response, using inhalation parameters (digital markers), clinical factors, and biomarkers.

Study Population: Adults > 18 years of age or older with severe persistent asthma as defined by ERS/ATS criteria that are currently receiving or awaiting approval for biologic therapies for asthma.

Phase: Open Label Real World Study

[figure not shown]
Description of Sites Enrolling Participants: All patients will be recruited from the Michigan Medicine Severe Asthma Clinics.

Description of Study Intervention: Maintenance inhaler (AirDuo® Digihaler™) and two rescue inhalers (ProAir® Digihaler™) use in Severe Asthma patients currently receiving or awaiting approval for biologic therapies for asthma.

Study Duration: 2 years, including approximately 3-month start-up, 6 months' recruitment period, 12 months follow-up of the last subject in (LSI), 3-month data cleaning and analysis.

Participant Duration: 12 months

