9 STATISTICAL CONSIDERATIONS

9.1 STATISTICAL HYPOTHESES

- Primary Efficacy Endpoint(s): Establish group-level daily/weekly baseline normative values for: (1) mean and median number of doses of ProAir® Digihaler™ and AirDuo® Digihaler™, and per-inhalation baseline normative values for (2) peak inspiratory flow (PIF), (3) inspiratory time and (4) volume. We will test the hypothesis that patient-specific baseline usage values are significantly different from usage values collected during or leading up to exacerbation events.
- Secondary Efficacy Endpoint(s): 1. Test the hypothesis that imminent exacerbation events can be predicted using Digihaler™ inhalation parameter measurements. 2. Test the hypothesis that PIF is linearly (or non-linearly) related to FVC and FEV1. Test the hypothesis that there exists a threshold for change in PIF that is associated with a clinically meaningful change (>10%) in lung function. 3. Test the hypothesis that patients with low, moderate, and high adherence to maintenance inhalers have significantly different asthma outcomes. 4. Test the hypothesis that non-responders, partial, and complete responders have significantly different Digihaler™ inhalation parameters. 5. Test the hypothesis that future response to biologics can be predicted using clinical, biological, and digital (inhalation) markers.

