9.4.3 ANALYSIS OF THE SECONDARY ENDPOINT(S)

1. To develop an algorithm that can identify probable imminent exacerbation events using Digihaler™ inhalation parameter measurements, we will compare the performance of several different machine learning regression models. Since we expect our training set to be relatively small with a low event rate, we plan to use the entire inhalation parameter dataset for model training but will employ repeated k-fold cross-validation to reduce variance (over-fitting) and include non-linear features to reduce bias (under-fitting). Examples of features that could be computed and included in this model include but are not limited to: difference between current value and patient-specific 7-day moving average, difference between current value and patient-specific 24-hour moving average, 7-day sample entropy, 24-hour sample entropy, difference in Min-Max over last 24 hours, etc.

A logistic regression model would treat the outcome (exacerbation) as a binary (Yes/No) event. The output of this model would be a daily probability between 0 and 1 that an exacerbation event will occur within a certain period of time. Different models will be fit for different periods of time (e.g., 24, 48, 72 hours) and the performance of each model assessed and compared to others. A recurrent event survival model would treat the exacerbations as discrete events in time. The output of this model would be the predicted time (e.g., in decimal days or hours) until the next event. Other models may include convolutional and/or recurrent neural networks (RNN) with LSTM or GRU architecture with varied numbers of hidden layers.

2. To determine whether and how PIF is associated with FEV1 and FVC, we assess the linearity and strength of the relationship using scatter plots, calculate the paired correlations (Pearson, Kendall, and Spearman), and compute univariate linear regression equations with PIF as the predictor and FEV1 or

FVC as the response. If non-linearity is found, we will determine the appropriate PIF transformation or polynomial term to use in the regression. Regression summary statistics (e.g., R-squared, Mean Absolute Error, Coefficients, and p-values) will be reported.

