9.4.9 EXPLORATORY ANALYSES

We plan to conduct extensive exploratory analyses including but not limited to: data cleaning and aggregation, outlier analysis, multicollinearity (correlation) analysis, sex effect analysis, age effect analysis, time series analysis, unsupervised cluster analysis, univariate testing (T-tests, Fisher's Exact Test, Wilcoxon Test, Chi-Squared Test, Tukey's Honest Significant Difference (HSD) Test), multivariable linear and non-linear regression, feature creation and selection for machine learning models, feature scaling and centering, training machine learning models using repeated k-fold cross-validation, and extensive data visualization for correlations and time series analysis.

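### The exacerbation algorithm's performance is defined on its own training data; neither out-of-fold reporting nor the cross-validation fold unit is stated

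*Combined protocol and SAP*

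**What the plan says.** Synopsis 1.1, Exploratory Endpoint 11, describes a confusion matrix summarising the algorithm's "performance on training dataset and from which performance statistics (accuracy, sensitivity, specificity, etc.) can be computed". The exploratory part of the table in section 3 uses the same words.

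Section 9.4.3, item 1, sets out the modelling: "we plan to use the entire inhalation parameter dataset for model training but will employ repeated k-fold cross-validation to reduce variance (over-fitting". It foresees several prediction windows (24, 48 and 72 hours are given as examples), with "the performance of each model assessed and compared to others". For the logistic version it says: "The output of this model would be a daily probability between 0 and 1 that an exacerbation event will occur". Neural networks are also allowed: "Other models may include convolutional and/or recurrent neural networks (RNN) with LSTM or GRU architecture with varied numbers of hidden layers". Section 9.4.9 mentions "training machine learning models using repeated k-fold cross-validation".

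The endpoint is listed as exploratory. Its aim is nevertheless Secondary Objective 1 in the Synopsis ("To determine the predictive value of inhalation parameters") and the first secondary hypothesis in 9.1 ("Test the hypothesis that imminent exacerbation events can be predicted using").

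**The concern.** A model scored on the rows used to fit it looks better than it will on new data, even when the features carry no information. The only places that name the evaluation data name the training data. An analyst could cross-validate while fitting, tabulate resubstitution results, and be in full compliance with the protocol. The resulting sensitivity and specificity could not answer secondary hypothesis 1.

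The missing fold unit matters for a related reason. With daily predictions, rows from one patient are correlated. If rows rather than patients are allocated to folds, the same patient sits on both sides of the split, and part of the optimism survives in figures that are labelled cross-validated.

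**Working it through.** **1. Where evaluation data are named**

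| Place | What it says about performance |
|---|---|
| 1.1 Endpoint 11; section 3 | Matrix on the training dataset |
| 9.4.3 item 1 | Whole dataset used for training; cross-validation to limit over-fitting; models compared, data for the comparison not named |
| 9.4.3 item 5 | Same approach for the responder model |
| 9.4.9 | Cross-validation as part of training |
| 4.2 and 9.2 | AUROC above 0.65 has a CI that excludes 0.5; source of the predictions not named |

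No section mentions out-of-fold predictions, a test set, the fold unit, k, the number of repeats or a cut-off rule.

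**2. The plan's own AUROC figure (4.2, 9.2)**

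Inputs: 100 patients and a 50% event rate, so n1 = n0 = 50, and A = 0.65. The Hanley-McNeil variance is [A(1−A) + (n1−1)(Q1−A²) + (n0−1)(Q2−A²)] / (n1·n0), where Q1 = A/(2−A) = 0.4815, Q2 = 2A²/(1+A) = 0.5121 and A² = 0.4225.

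- Numerator: 0.2275 + 49 × 0.0590 + 49 × 0.0896 ≈ 7.509
- SE = √(7.509/2500) = 0.0548
- 95% CI: 0.65 ± 1.96 × 0.0548 = 0.543 to 0.757

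The statement reproduces. It treats each patient as one independent observation and makes no allowance for optimism.

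**3. Null simulation: set-up**

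The documents give 100 patients, 48 weeks to the end-of-study visit (336 days) and a 72-hour window. The following are assumptions:

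- 1 exacerbation per patient-year, with gamma frailty of variance 1 and a 14-day minimum gap
- 6 or 20 features unrelated to outcome: AR(1) noise with rho 0.5 and 60% of variance between patients, half raw and half differenced from the prior 7-day mean

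This gives 100 × 336 = 33,600 rows, of which about 258 (0.8%) are positive. True AUROC is 0.50. Training performance is compared with 5-fold cross-validation by patient. The base case has 400 replicates and other logistic cells 200; the Monte Carlo SE of mean AUROC is at most 0.004.

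**4. Logistic results**

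| Quantity | 6 features | 20 features |
|---|---|---|
| Mean training AUROC | 0.57 | 0.63 |
| Mean AUROC out of fold, by patient | 0.50 | 0.50 |
| Sensitivity + specificity − 1, training | 0.12 | 0.20 |
| Same, out of fold, cut-off set in training folds | 0.00 | 0.00 |
| 95% CI for AUROC above 0.5, training | 59–64% | 100% |
| Same, out of fold | 2–6% | 5–10% |

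With rates of 0.5 to 2 per year, training AUROC ranged from 0.55 to 0.67. With a 24-hour window it was 0.58 and 0.65.

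The last two rows use a patient-clustered variance and have a nominal error of 2.5%. Their ranges come from two versions: fold-averaged AUROC with a z interval (400 replicates), and pooled 3 × 5-fold predictions with a t interval (250 and 200 replicates).

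**5. Networks**

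A feed-forward 64/32 network stood in for the convolutional and recurrent types, with 6 to 10 replicates per setting (SE of training AUROC at most 0.027). Mean training AUROC for 6 and 20 features:

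- weight decay 1.0: 0.57 and 0.62
- early stopping: 0.51 and 0.56 (accuracy rule), or 0.62 and 0.66 (log-loss rule)
- unregularised: 0.82 and 1.00

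Out of fold by patient, the range was 0.50–0.53.

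**6. Fold unit**

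For logistic models with rows as folds (40 replicates, SE at most 0.008), AUROC was 0.55 and 0.61 with raw features, and 0.52 and 0.55 with differenced features. Patient-level folds gave 0.50–0.51.

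**7. Different assumptions**

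A second null simulation used 100 patients × 60 days, about a 3% daily event rate, a between-patient log-odds SD of 1.5, and 30 replicates. Logistic models with 5, 10 and 20 features gave:

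- training AUROC: 0.61, 0.64, 0.70
- row folds: 0.59, 0.60, 0.64
- patient folds: 0.51, 0.49, 0.52

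A 15-nearest-neighbour model gave 0.90–0.93 in training, 0.62–0.70 with row folds and 0.50–0.51 with patient folds.

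**The case against.** **Cross-validation is already planned.** With a single dataset, the training-dataset wording may mean only that there is no external test set. This stands as a reading of intent. It does not alter the endpoint definition, and 9.4.3 and 9.4.9 describe cross-validation as part of fitting, not as the source of reported results.

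**The error rates rest on an assumed test.** The documents name none, so this is correct. A confidence interval that excludes 0.5 is nevertheless the benchmark used in 4.2 and 9.2. If the criterion were a training AUROC above 0.65, a repeat of the base case (100 replicates) exceeded it in 0% (6 features) and 19% (20 features) of null data sets. The harm therefore depends on the criterion.

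**The raw features inflate the result.** The example features in 9.4.3 are mostly patient-specific differences. With differenced features only, training AUROC was 0.555 and 0.60, and the interval still lay above 0.5 in 70% and 100% of null data sets (100 replicates). The objection reduces the optimism slightly and leaves the false claims. It does show that the fold-unit effect is small for such features (0.52 and 0.55).

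**Patient-level folds may not match the use.** If the aim is to monitor patients already known to the model, time-blocked folds are defensible. That is a fair point, but Secondary Objective 1 speaks of prediction in a population, and the plan states no unit at all.

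**The remedy is imperfect and the endpoint exploratory.** With 20 features the out-of-fold error is still 5–10% against 2.5%, although training data give 100%. The exploratory label lowers the weight of the point. The same analysis nevertheless serves a secondary objective and a secondary hypothesis.

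**Conclusion.** The concern holds. As written, the endpoint prescribes resubstitution performance, and nothing elsewhere in the plan overrides it. This is a defect in the stated definition; it does not prove that only apparent performance will be reported.

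The shift in AUROC is modest for logistic models and for networks with weight decay or early stopping. Even so, it makes uninformative logistic models look predictive in most or all null data sets. It is large only for unregularised networks, which 9.4.3 neither specifies nor excludes.

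The sizes depend on the assumed exacerbation rate, frailty, feature count and correlation, on the assumed interval test, and, for networks, on few replicates of a stand-in architecture. The direction was the same under both sets of assumptions. Confidence is high on the gap in the text; the magnitudes are illustrative.

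**What to change.** In Synopsis 1.1, Endpoint 11, and in the matching row of section 3, replace the reference to the training dataset with: *out-of-fold performance from repeated k-fold cross-validation, with all records of a patient in the same fold.*

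In 9.4.3, item 1, add: *Reported performance is computed from these out-of-fold predictions. Feature selection, tuning and choice of cut-off are done inside the training folds. Training performance may be shown beside it, labelled as apparent.*

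The same sentences could be added to item 5 for the responder model; this is optional and not part of the error.

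The cost is wording in three places and some computing time, with no change to data collection or sample size. Reported performance will be less favourable.

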9.2 SAMPLE SIZE DETERMINATION

Sample size calculations were based on peak inspiratory flow measurements.

Based on population-based estimates of peak inspiratory flow:

<https://www.ncbi.nlm.nih.gov/pmc/articles/PMC5328129/> The mean was 115 and standard deviation was 15. With a 100-patient sample, 95% CI of our estimate of the mean would be plus or minus 3, e.g. 115 (95 CI 112 – 118).

The machine learning model will be performed based on the most common measure to evaluate performance which is discrimination that is assessed by an AUROC. If we have a 100-patient sample and assume a 50% event rate (<http://www.biosoft.hacettepe.edu.tr/easyROC>), we would have adequate power to conclude that a model with an AUROC performance of > 0.65 has confidence intervals that won't cross 0.5 (which would be a model that is no better than chance).

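### Accuracy says almost nothing about the daily exacerbation algorithm at a low event rate, and the plan names no positive predictive value, cut-off or comparison measure for it

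*Combined protocol and SAP*

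**What the plan says.** The Synopsis (section 1.1, Exploratory Endpoint 11) defines the product as "Algorithm that produces a daily asthma exacerbation probability given a set of baseline and current inhalation parameters". The reported summary is "A confusion matrix summarizing the algorithm's performance on training dataset", and from it "performance statistics (accuracy, sensitivity, specificity, etc.) can be computed". The table in section 3 repeats this under the exploratory objectives.

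Section 9.4.3 item 1 describes the modelling. It states that "we expect our training set to be relatively small with a low event rate", without giving a rate. All the data are used for training, with repeated k-fold cross-validation; whether folds are formed by patient or by patient-day is not said. On choosing a horizon it says "Different models will be fit for different periods of time (e.g., 24, 48, 72 hours) and the performance of each model assessed and compared", again without naming the measure.

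Sections 4.2 and 9.2 name the area under the ROC curve (AUROC) as the measure for the machine learning model, sized as follows: "If we have a 100-patient sample and assume a 50% event rate".

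I found no positive predictive value (PPV), precision-recall measure, calibration measure, false-alarm rate or rule for the probability cut-off for the daily model.

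**The concern.** The algorithm makes one prediction per patient per day, and on nearly all of those days no exacerbation follows. Accuracy, the first statistic listed, is then driven by the share of event-free days and hardly responds to whether the model finds exacerbations.

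A confusion matrix also needs a cut-off. None is given, so the matrix could sit anywhere between almost no alarms and very many.

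Section 2.1 gives the purpose as earlier detection, so that patients and clinicians can act. Whether that is feasible depends largely on how many alarms are false for each true one, and the plan does not ask for that figure. With several model families, three example horizons and no named measure, the measure could also be chosen after the results are seen.

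**Working it through.** **The plan's own figure.** With 50 events and 50 non-events, the Hanley-McNeil standard error of an AUROC of 0.65 is 0.0548. The 95% CI is 0.65 ± 1.96 × 0.0548 = 0.543 to 0.757, which excludes 0.5 as stated. That calculation is for 100 patients at a 50% event rate. It does not describe a daily model with a low event rate.

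**Inputs for the daily model.** Windows of 24, 48 and 72 hours (w = 1, 2, 3 days) come from section 9.4.3. The exacerbation rate r is not in the documents; I assume 0.5 to 3 per patient-year. Sensitivity (Se) 80% and specificity (Sp) 90% are illustrative assumptions. Alarm means only that the predicted probability passes the cut-off.

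**Formulas.**
- Share of event days: p = r × w / 365.25
- Never-alarm accuracy: 1 − p (sensitivity 0%, specificity 100%, AUROC 0.5)
- Model accuracy: p × Se + (1 − p) × Sp
- PPV: p × Se / [p × Se + (1 − p)(1 − Sp)]
- False-alarm days per patient-year: (1 − Sp)(1 − p) × 365.25

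| r per year | Window | p | Never-alarm accuracy | Model accuracy | Model PPV | False-alarm days |
|---|---|---|---|---|---|---|
| 0.5 | 24 h | 0.14% | 99.86% | 89.99% | 1.1% | 36.5 |
| 0.5 | 72 h | 0.41% | 99.59% | 89.96% | 3.2% | 36.4 |
| 1.5 | 24 h | 0.41% | 99.59% | 89.96% | 3.2% | 36.4 |
| 1.5 | 48 h | 0.82% | 99.18% | 89.92% | 6.2% | 36.2 |
| 1.5 | 72 h | 1.23% | 98.77% | 89.88% | 9.1% | 36.1 |
| 3 | 24 h | 0.82% | 99.18% | 89.92% | 6.2% | 36.2 |
| 3 | 72 h | 2.46% | 97.54% | 89.75% | 16.8% | 35.6 |

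**When a model beats never-alarm on accuracy.** This requires p × Se + (1 − p) × Sp > 1 − p, that is p × Se > (1 − p)(1 − Sp), which is the same as PPV > 50%. At Se 80%, Sp must exceed 1 − 0.8p/(1 − p): 99.89% at r = 0.5 and 24 h, and 97.98% at r = 3 and 72 h. Some models do pass. With Se 50% and Sp 99% at r = 3 and 72 h, accuracy is 97.79% against 97.54%, with PPV 55.8%.

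**Effect of the horizon on accuracy.** Accuracy = Sp + p(Se − Sp). At r = 1.5, a model with Se 80% and Sp 90% goes from 89.96% (24 h) to 89.88% (72 h). A model with Se 90% and Sp 80% goes the other way, from 80.04% to 80.12%.

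**The case against.** The text says that statistics can be computed, and its list is open-ended. A reader might infer that accuracy is the criterion by which the algorithm is judged. The documents do not say so: accuracy is one example, and section 9.4.3 speaks only of performance.

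The planned statistics would also expose a rule that never alarms. Its sensitivity is 0%, and its AUROC is 0.5, exactly the value that sections 4.2 and 9.2 want to exclude.

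A reader might further infer that the plan hides the false alarms. It does not: they are the false-positive cell of the planned matrix, and both PPV and the 36 days follow from the same table.

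Finally, the endpoint is exploratory, and section 2.1 leaves clinical utility to future trials.

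All of this stands, and it limits the point to reporting and model comparison. It does not remove it. Sensitivity, specificity and AUROC do not depend on prevalence, so at 80% and 90% a model can look good while 83 to 99% of its alarms are false, unless someone does the extra calculation. Predicting exacerbations is also Secondary Objective 1 in the Synopsis, the first secondary hypothesis in section 9.1 and item 1 of section 9.4.3, although its algorithm endpoint is labelled exploratory.

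**Conclusion.** The point holds as a gap in how the daily algorithm is summarised and compared. For 0.5 to 3 exacerbations per patient-year and windows of 24 to 72 hours, never-alarm accuracy is 97.5 to 99.9%. A model with 80% sensitivity and 90% specificity scores about 90%, with a PPV of about 1 to 17% and about 36 false-alarm days per patient-year. The rates and the sensitivity and specificity pair are assumptions; the plan says only that the event rate is low.

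Two further inferences go too far. Accuracy does not automatically favour the shortest horizon: the direction depends on whether specificity or sensitivity is larger, and in the examples above the difference is 0.08 percentage points. Nor is validation absent, since cross-validation is planned. What is unsettled is that the endpoint fills the matrix from the training dataset, where every statistic would be optimistic, and does not say that the cross-validated predictions are to be used.

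**What to change.** In Endpoint 11 (Synopsis and section 3) and section 9.4.3 item 1:

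1. Do not use accuracy to assess or compare the daily models.
2. Build the confusion matrix from cross-validated predictions with whole patients held out, not from the training fit. The example features in section 9.4.3 use a patient's own recent data, so they can still be computed for a held-out patient.
3. Report sensitivity, PPV, false-alarm days per patient-month and area under the precision-recall curve, together with AUROC. Show the event-day prevalence for each horizon beside them, because that is the PPV and precision-recall area expected from uninformative alarms.
4. Prespecify the analysis cut-off as a fixed false-alarm rate. This is a rule for the analysis only, with its value chosen by the investigators before the outcome data are examined.
5. Compare the 24, 48 and 72 hour models on the share of exacerbations detected at that same rate. A longer window gives more chances of a hit, so add what random alarms would detect. For example, independent alarms on 10% of days would precede 1 − 0.9 = 10% of exacerbations at 24 h and 1 − 0.9³ = 27.1% at 72 h.

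The cost is a few lines of text, folds formed by patient, and some extra summaries of predictions that the planned cross-validation already yields. No new data are needed. The drawback is that the reported figures will look less favourable.
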